9.3. Randomization

Randomization will take place at Visit 2 (Week 0) with IWRS system which is described in the eCRF. Patients will be randomized into three equal groups (1:1:1) using the IWRS system (155 patients per group).

9.4. Statistical methods

Statistical analysis will be performed according to the Statistical Analysis Plan created and finalized before the database lock.

The Safety Population will consist of all randomized patients who received at least one dose of the study product.

The Full Analysis Set (FAS) will consist of all randomized patients who received at least one dose of the study product and have at least one post-baseline assessment of the efficacy parameters.

Per Protocol set (PP) will consist of all FAS patients who completed study treatment and had no significant protocol violations.

Also, secondary endpoint analysis will be performed in the following subgroups:

- Patients with IBS
- Patients with other functional bowel diseases
- Patients with constipation
- Patients with diarrhea
- Patients with both constipation and diarrhea
- Patients with neither constipation nor diarrhea

9.5. Patient distribution, demographic and baseline characteristics

Patient distribution, demographic and baseline characteristics will be presented using descriptive statistics. The number and percentage of patients receiving concomitant medication will be presented in frequency tables according to the ATC class level 2 and 4. The number and percentage of patients with comorbidities and preceding conditions will also be specified.

9.6. Study drug intake

Information on dosage, including daily doses, duration of effect and total doses, will be presented in a descriptive way for each treatment group.

Confidential Page 68 of 94

9.7. Efficacy analysis

9.7.1. Primary efficacy end point

• Change from baseline of sum of NRS-11 abdominal pain and bloating/flatulence intensity scores after 4 weeks of treatment.

The baseline abdominal pain and bloating/flatulence intensity will be determined as the average of the NRS-11 daily assessment during 7 days before randomization (weekly average of last week of screening and run-in period). The Week 4 assessment is the same (data from last 7 days of the corresponding week)..

9.7.2. Primary end points analysis

The FAS will be the main sample for efficacy assessment in this study performed to confirm superiority. Additional analysis of the primary efficacy endpoint will be performed in the per protocol (PP) set.

For the difference of changes in sum scores of NRS-11 pain and bloating/flatulence intensities after 4 weeks of treatment versus baseline between the groups Mebeverine+Simethicone versus Duspatalin® and Mebeverine+Simethicone versus Espumisan®, a two-sided 95% confidence interval (CI) will be constructed, which is equivalent to a 97.5% one-sided CI. The confidence interval will be constructed using ANCOVA, which will include treatment and site as fixed effect, and baseline parameter will be included in the model as covariate. To test the hypothesis of superiority of the FDC Mebeverine+Simethicone versus every comparator (Duspatalin® and Espumisan®), the upper confidence limit will be used. The null hypothesis (H₀: no difference in change from baseline of sum of bloating/flatulence and pain scores between the FDC and corresponding comparator, will be rejected in favor of the alternative hypothesis (H_a: larger change from baseline of sum of bloating/flatulence and pain scores in the fixed-dose combination Mebeverine+Simethicone group) only if the upper limit of two-sided 95% CI does not contain the value 0. In addition the study will be considered successful in case both superiority hypothesizes are proven, i. e. upper limit of two-sided 95% CI does not contain the value 0 for both constructed confidence intervals. In this case, the conclusion will be drawn on the fixed-dose combination of Mebeverine+Simethicone to be superior versus Duspatalin® (mebeverin) and Espumisan® (simethicone) for the decrease of both pain and bloating/flatulence intensity.

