- Patients with other functional bowel diseases
- Patients with constipation
- Patients with diarrhea
- Patients with both constipation and diarrhea

Patients with neither constipation nor diarrhea.

Primary efficacy endpoint analysis

The FAS will be the main sample for efficacy assessment in this study performed to confirm superiority. Additional analysis of the primary efficacy endpoint will be performed in the per protocol (PP) set.

For the difference of changes in sum scores of NRS-11 pain and bloating/flatulence after 4 weeks of treatment versus baseline between groups Mebeverine+Simethicone versus Duspatalin® Mebeverine+Simethicone versus and Espumisan®, a two-sided 95% confidence interval (CI) will be constructed, which is equivalent to a 97.5% one-sided CI. The confidence interval will be constructed using ANCOVA, which will include treatment and site as fixed effect, and baseline parameter will be included in the model as covariate. To test the hypothesis of superiority of the FDC Mebeverine+Simethicone versus every comparator (Duspatalin® and Espumisan®), the upper confidence limit will be used. The null hypothesis (H₀: no difference in change from baseline of sum of bloating/flatulence and pain scores between the FDC and corresponding comparator, will be rejected in favor of the alternative hypothesis (H_a: larger change from baseline of sum of bloating/flatulence and pain scores in the fixed-dose combination Mebeverine+Simethicone group) only if the upper limit of two-sided 95% CI does not contain the value 0. In addition the study will be considered successful in case the both superiority hypothesizes are proven, i. e. upper limit of two-sided 95% CI does not contain the value 0 for both constructed confidence intervals. In this case, a conclusion will be drawn on the fixed-dose combination of Mebeverine+Simethicone is superior versus Duspatalin® (mebeverin) and Espumisan® (simethicone) for the pooled decrease of pain and bloating/flatulence intensity.

Secondary endpoint analysis

Intergroup comparisons will also be performed for secondary efficacy endpoints using the χ^2 /Fisher exact test and 95% confidence intervals for differences in proportions will be given. Additionally, the proportion of patients with reduced severity of pain in the bowel region and bloating/flatulence during each week of the 4-week treatment period charts will be constructed.

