3.5.3. Efficacy and safety assessment parameters

Mebeverine and Simethicone affect two different key symptoms in patients with functional diseases of the colon: pain and bloating/flatulence. As the assessed symptoms are interrelated it was decided to use a coprimary end point (change of sum of NRS-11 every symptom intensity scores) as such approach is widely used in clinical studies in patients with FBD.⁴⁸

The study will also evaluate secondary efficacy parameters based on a numerical rating scale (NRS-11): the rate and degree of clinical symptoms relief, changes in the quality of life during treatment, need for additional antispasmodics.

Although the previous studies and the long-term use of Mebeverine and Simethicone in clinical practice demonstrated a favorable safety profile comparable to that of placebo, the study provides a detailed assessment of the product safety, including physical examination, vital signs, laboratory blood tests and urinalysis (hematology and clinical chemistry, urinalysis) before and after the study treatment. Women of child-bearing potential will undergo a urine pregnancy strip test before the study.

Confidential Page 32 of 94

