9.7.4. Secondary efficacy end points analysis

Intergroup comparisons will also be performed for secondary efficacy endpoints using the χ^2 /Fisher exact test and 95% confidence intervals for differences in proportions will be given. Additionally, the proportion of patients with reduced severity of pain in the bowel region and bloating/flatulence during each week of the 4-week treatment period charts will be constructed.

ANCOVA model, which will include treatment and site as fixed effect, and baseline value as covariate, will be used for continuous covariates comparison presenting treatment effect estimates and associated 95% CIs.

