4.2.1 Primary Efficacy Analysis

The primary efficacy endpoint is:

- Change from baseline of sum of NRS-11 abdominal pain and bloating/flatulence intensity scores after 4 weeks of treatment.

The baseline abdominal pain and bloating/flatulence intensity will be determined as the average of the NRS-11 daily assessment during 7 days before randomization (weekly average of last week of screening and run-in period, in other words, the average of - 6 to 1 days). The Week 4 assessment is the same (data from last 7 days of the corresponding week in the case duration of treatment 28 days: 23 to 29 days or data from the last 7 days before the last treatment day inclusively in the case duration of treatment did not equal 28 days.

11

For the difference of changes in sum scores of NRS-11 pain and bloating/flatulence intensities after 4 weeks of treatment versus baseline between the groups Mebeverine+Simethicone versus Duspatalin® and Mebeverine+Simethicone versus Espumisan®, a two-sided 95% confidence interval (CI) will be constructed, which is equivalent to a 97.5% one-sided CI.

The confidence interval will be constructed using ANCOVA, which will include treatment and site as fixed effect, and baseline parameter will be included in the model as covariate.

ANCOVA analysis will be performed using SAS code for the analysis:

```
ods output LSmeans=LSMeans;
ods output Diffs=CL;
proc mixed data= <dataset_name> ;
        CLASS <treatment> <site>;
        MODEL <change from bl> = <treatment> <site> <baseline>;
        lsmeans <treatment> / pdiff cl;
run;
ods output close;
```

To test the hypothesis of superiority of the FDC Mebeverine+Simethicone versus every comparator (Duspatalin® and Espumisan®), the upper confidence limit will be used.

The null hypothesis (H₀: no difference in change from baseline of sum of bloating/flatulence and pain scores between the FDC and corresponding comparator, will be rejected in favor of the alternative hypothesis (Ha: larger change from baseline of sum of bloating/flatulence and pain scores in the fixed-dose combination Mebeverine+Simethicone group) only if the upper limit of two-sided 95% CI does not contain the value 0.

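### Protocol 9.7.2 claims superiority on both pain and bloating from a test of their sum alone; the synopsis and SAP claim only the pooled decrease

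*Protocol*

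**What the plan says.** Protocol 9.7.1 defines one primary variable: "Change from baseline of sum of NRS-11 abdominal pain and bloating/flatulence intensity scores after 4 weeks of treatment". In 9.7.2 the alternative hypothesis is also on the sum: "larger change from baseline of sum of bloating/flatulence and pain scores in the fixed-dose combination Mebeverine+Simethicone group". The success rule rests on those hypotheses, one per comparator: "the study will be considered successful in case both superiority hypothesizes are proven".

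The documents then draw two different conclusions from the same result:

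- Protocol 9.7.2: superiority "for the decrease of both pain and bloating/flatulence intensity".
- Protocol synopsis (Primary efficacy endpoint analysis) and SAP 4.2.1: superiority "for the pooled decrease of pain and bloating/flatulence intensity".

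Pain alone and bloating alone are secondary endpoints (Protocol 9.7.3, SAP 4.2.2). For continuous secondary endpoints the protocol plans an ANCOVA, which "will be used for continuous covariates comparison presenting treatment effect estimates and associated 95% CIs". These results do not enter the success rule, and neither document specifies multiplicity control for them.

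**The concern.** The word both in 9.7.2 refers to the two symptoms, since the two comparators are named separately in the same sentence. Read as written, a win on the sum licenses a claim on pain and a claim on bloating, each against mebeverine and against simethicone. That is four statements, and the primary analysis tests none of them.

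This matters more than usual here because the product is a combination. Protocol 3.5.3 states: "Mebeverine and Simethicone affect two different key symptoms in patients with functional diseases of the colon: pain and bloating/flatulence". On that reasoning, adding simethicone to mebeverine could move mainly bloating, and adding mebeverine to simethicone mainly pain. An uneven split is therefore a natural expectation under the protocol's own rationale. Protocol 3.8.1 relies on the primary endpoint, with relevant secondary endpoints, to prove each component's contribution, so the exact claim is important. Sections 3.5.1, 3.5.3 and 3.8.1 also call the single sum a co-primary endpoint, which invites a per-symptom reading.

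**Working it through.** **Inputs from the documents (Protocol 9.2).** Difference of 1.0 on the sum, SD 2.5, alpha 0.05 two-sided, 90% power per comparison, 132 evaluable per arm, 15% drop-out, 155 randomized per arm, overall power about 80%.

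**The plan's own figures.**

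- n per arm = 2 × (1.960 + 1.282)² × 2.5² / 1.0² = 131.3, rounded up to 132. This agrees.
- 132 / 0.85 = 155.3, against 155 stated. This agrees within rounding.
- SE of a difference = 2.5 × √(2/132) = 0.3077, and 1.0 / 0.3077 = 3.25.
- Power per comparison = Φ(3.25 − 1.96) = 0.901.
- Both comparisons: 0.90² = 0.81 if treated as independent. It is 0.835 with the correlation of 0.5 that the shared combination arm induces. Both are consistent with about 80%.

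**Dependence on the split.** Write the benefit as d(pain) + d(bloating) = 1.0. The test statistic for the sum has mean 1.0 / 0.3077 for any split, so the win probability is 0.835 for any split. It stays at 0.835 even if pain is 0.25 points worse and bloating 1.25 points better.

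**What the separate symptom tests would show.** The documents give neither the split nor the correlation (ρ) between the two symptoms, so both are assumed. The symptom SDs are taken as equal and set so that the sum has SD 2.5: SD = 2.5 / √(2(1+ρ)) = 1.55, 1.44 and 1.36 for ρ = 0.3, 0.5 and 0.7. Each symptom is tested at two-sided 5% in favour of the combination, with 1,000,000 simulated trials per scenario.

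| Assumed benefit of the combination | P(win on the sum, both comparators) | Symptom result among wins (ρ = 0.3, 0.5, 0.7) |
|---|---|---|
| Bloating only vs mebeverine, pain only vs simethicone | 0.835 | all four tests significant: 0.16%, 0.23%, 0.33% |
| Bloating only vs both comparators | 0.835 | pain significant vs both: 0.57%, 0.54%, 0.54% |
| 0.5 on each symptom vs both comparators | 0.834 | all four tests significant: 50%, 65%, 79% |

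A separate simulation of 400,000 trials agrees. For the equal split it gave unconditional probabilities of 0.420, 0.543 and 0.655 that all four tests succeed. Divided by win probabilities of 0.835, 0.834 and 0.834, these give 50%, 65% and 79%.

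**The case against.** The strongest reply is that this is one phrase, contained by the rest of the plan. The hypotheses in 9.7.2 name the sum, the individual symptoms are listed as secondary, the protocol says analysis follows the SAP, and the SAP has the narrower wording. The phrase could be loose English for the combined score. This limits the seriousness but does not remove the conflict. Nothing in either document says that the SAP's conclusion overrides the protocol's.

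Objections to the figures are partly right:

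- The equal-split row shows the power of the component tests, not an error. In that scenario the combination really is better on both symptoms, so the conclusion would be true in every win.
- The bloating-only row assumes no pain benefit even against simethicone, which the rationale in 3.5.3 does not suggest. That rationale supports the complementary row. The small percentage in the bloating-only row is essentially the joint false-positive rate of two null pain tests.
- The protocol also argues that the symptoms are interrelated and that each drug may affect both, so exact zeros are illustrative.

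The central result needs none of these scenarios: the win probability does not depend on the split.

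**Conclusion.** The concern holds. Protocol 9.7.2 attaches to the primary test a conclusion that the test cannot support, and it disagrees with the synopsis and SAP 4.2.1. With 1.0 point on the sum, SD 2.5 and 132 per arm, the 9.7.2 conclusion would be drawn with probability about 0.835 whether or not each symptom improves. Under the assumed complementary split it would be drawn about 83% of the time, although the combination would have no advantage on one symptom against each comparator. The win probability rests only on the plan's figures; the symptom-level percentages rest on the assumed splits, correlations and equal SDs.

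The primary test itself is sound. The defect is in the permitted claim, and it should be corrected because that claim is the trial's headline conclusion.

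**What to change.** In Protocol 9.7.2, replace the phrase with the synopsis and SAP wording, "for the pooled decrease of pain and bloating/flatulence intensity". Report the planned pain and bloating ANCOVAs beside the primary result with estimates and 95% confidence intervals, labelled as supportive secondary evidence because no multiplicity control is specified. Endpoint, model, alpha and sample size stay as they are; the claim becomes narrower.

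A minor clarification can be made at the same time and carries no weight in the verdict. Both documents reject the null hypothesis "only if the upper limit of two-sided 95% CI does not contain the value 0". A single limit cannot contain a value, and the direction of subtraction is not stated, although the intended one-sided 2.5% test is clear. State in the synopsis, 9.7.2 and SAP 4.2.1 that the difference is combination minus comparator in LS mean change (Week 4 minus baseline), with superiority if the upper limit is below 0 for both comparisons. Write explicit contrasts in that direction in the SAP code.

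The cost is one phrase in the protocol, one clarifying sentence in each place, and a small edit to the SAP program.

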9.7.3. Secondary efficacy end points

- Change from baseline of NRS-11 pain intensity after 4 weeks of treatment
- Proportion of patients with the NRS-11 pain intensity reduction of ≥30% versus baseline during at least 50% of treatment weeks over treatment period
- Proportion of patients with the NRS-11 pain intensity reduction of $\geq 50\%$ versus baseline during at least 50% of treatment weeks over treatment period.
- Proportion of patients with the abdominal pain assessed in the Patient Dairy completely resolved during at least 50% of treatment weeks over treatment period (NRS-11 0 assessment).
- Change from baseline of NRS-11 bloating/flatulence intensity after 4 weeks of treatment
- Proportion of patients with the NRS-11 bloating/flatulence intensity reduction of ≥30% versus baseline during at least 50% of treatment weeks over treatment period.
- Proportion of patients with the NRS-11 bloating/flatulence intensity reduction of \geq 50% versus baseline during at least 50% of treatment weeks over treatment period.

Confidential Page 69 of 94

- Proportion of patients with the bloating/flatulence assessed in the Patient Dairy completely resolved during at least 50% of treatment weeks over treatment period (NRS-11 0 assessment).
- For patients with constipation: proportion of patients with any increase in number of CSBM per week versus baseline during at least 50% of treatment weeks.
- For patients with diarrhea: proportion of patients with any decrease in the number of days per week with at least one stool consistency of Type 6 or Type 7 BSS versus baseline during at least 50% of treatment weeks.
- Change in number of days per week during study treatment period when drotaverine was taken.
- Change in quality of life evaluation using IBSQOL questionnaire versus baseline.

The baseline abdominal pain and bloating/flatulence intensity will be determined as average of the worst daily episodes NRS-11 assessment during 7 days before randomization (last week of screening and run-in period). The data from last week of screening and run-in period will be also used for baseline assessment of stool frequency and consistency and number of days of drotaverin intake. Week 1, Week 2, Week3 and Week 4 assessments are the same (data from the last 7 days of the corresponding week).

9.7.4. Secondary efficacy end points analysis

Intergroup comparisons will also be performed for secondary efficacy endpoints using the χ^2 /Fisher exact test and 95% confidence intervals for differences in proportions will be given. Additionally, the proportion of patients with reduced severity of pain in the bowel region and bloating/flatulence during each week of the 4-week treatment period charts will be constructed.

ANCOVA model, which will include treatment and site as fixed effect, and baseline value as covariate, will be used for continuous covariates comparison presenting treatment effect estimates and associated 95% CIs.

9.8. Safety analysis

9.8.1. Safety end points:

• Safety will be assessed per treatment arm, based on the incidence and severity of AE and SAE, physical examination, vital signs and lab results.

9.8.2. Safety end points analysis

The safety sample will be used for the analysis of the safety and tolerability data.

Treatment Emergent Adverse Events (TEAEs) including AE and SAE will be presented by frequencies (number of patients with AEs and number of events) and are summarized by unique treatment (Mebeverine+Simethicone, Duspatali®, Espumisan®), primary System Organ Class (SOC) and Preferred terms (PT) and relation to the study drug and severity. Severity and drugevent relationship of the treatment emergent AEs are summarized separately.

Laboratory values and vital signs by visit and their changes from baseline will be summarized in tables of descriptive statistics. Abnormal values (according to the reference ranges) will be presented in frequency tables (low, normal and high values).

9.9. Procedures to record missing, not subject to analysis and dubious data

No missing data will be added. To analyze the efficacy endpoints the last observation carry forward (LOCF) will be used. To determine the sensitivity of the evaluation: first the patients with

Confidential Page 70 of 94

missing data will be analyzed, then the patients will be analyzed without replacing the missing data.

[figure not shown]

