4.2 Efficacy analysis

The FA subject sample will be used for the analysis of the efficacy data. Additionally, primary efficacy results analysis will be conducted on the PP sample as the sensitivity analysis. Descriptive statistics will be presented by treatment arm for all planned efficacy endpoints.

The PP subject sample analyses will be based on available data only and no missing data will be imputed.

The FA subject sample analyses will be based how on available data only so and data following the last observation carried forward (LOCF) approach will be used.All parameters will be summarized using descriptive statistics and listed.

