The baseline abdominal pain and bloating/flatulence intensity will be determined as the average of daily episodes NRS-11 assessment during 7 days before randomization (last week of screening and run-in period, in other words, the average of daily episodes from - 6 to 1 days). The data from the last week of screening and run-in period will be also used for baseline assessment of stool frequency and consistency and number of days of drotaverine intake. Week 1 (average of data 2 - 8 days), Week 2 (average of data 9 - 15 days), Week 3 (average of data 16 - 22 days) and Week 4 (average of data from the last 7 days of the corresponding week in the case duration of treatment 28 days: 23 to 29 days or data from the last 7 days before the last treatment day inclusively in the case duration of treatment did not equal 28 days).

The proportion of patients with the *Scale* reduction of $\geq A\%$ versus baseline during at least 50% of treatment weeks over treatment period must be calculated as:

$$\frac{n_T}{N_T}$$

where N_T is total number of patients in the treatment arm T, n_T is number of patients in the treatment arm T who had reduction of $\ge A\%$ versus baseline (week 0) during at least 2 of treatment weeks over treatment period: week 1, week 2, week 3, week 4). Reduction of $\ge A\%$ must calculate as:

$$Reduction_{i} = \frac{\overline{Scale_{Week_{i}}} - \overline{Scale_{Week_{0}}}}{\overline{Scale_{Week_{0}}}} \times 100 \ge A\%$$

The transformation formula used for the IBS-QOL total and scale scores is:

 $Score = \frac{The sum of the items - lowest possible score}{Possible raw score range} \times 100$

Where

lowest possible score = number of questions \times lowest possible score of the items

possible raw score range

= number of questions

 \times (upper possible score of the items - lowest possible score of the items)

The comparisons of treatment arms for secondary endpoints with "Proportion of patients with the..." type will be analyzed using Fisher exact test. The test will be performed by separately for for Mebeverine + Simethicone combination VS Duspatalin (mebeverin) and Mebeverine + Simethicone combination VS Espumisan (simethicone) comparisons.

Fisher exact test will be performed using following SAS code for the analysis:

```
PROC FREQ DATA = [dataset name];
  weight [frequency var] / ZEROS;
  tables [frequency var lvl 1/ frequency var lvl 2] * [Arm] / exact Fisher;
RUN;
```

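### On the ≥30% and ≥50% responder endpoints, one observed good week can satisfy a two-of-four-weeks rule, through LOCF or through the SAP's Week 4 window

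*Protocol*

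**What the plan says.** **Endpoints.** Protocol 9.7.3 lists four percentage-reduction responder endpoints: ≥30% and ≥50%, each for pain and for bloating/flatulence. Each must be met "versus baseline during at least 50% of treatment weeks over treatment period". SAP 4.2.2 makes this concrete: the reduction must be reached "during at least 2 of treatment weeks over treatment period: week 1, week 2, week 3, week 4", and the number of such patients is divided by all patients in the arm.

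**Missing data, protocol.** Section 9.9 opens with "No missing data will be added" and goes straight on to "To analyze the efficacy endpoints the last observation carry forward (LOCF) will be used". It exempts no endpoint. It closes with a sensitivity step, "then the patients will be analyzed without replacing the missing data".

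**Missing data, SAP.** Section 4.2 says of the FA sample: "The FA subject sample analyses will be based how on available data only so and data following the last observation carried forward (LOCF) approach". Of the Per Protocol (PP) sample it says: "The PP subject sample analyses will be based on available data only and no missing data will be imputed". Section 4.2.1 lists LOCF on the FA sample as the second sensitivity analysis of the primary endpoint. No sentence says which version is the main one for the responder endpoints, and none counts an unobserved week as non-response. The one failure rule, in SAP 4.2.1, concerns an ALT response, which is not an endpoint of this trial.

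**Weekly windows.** SAP 4.2.2 sets Week 1 as Days 2–8, Week 2 as Days 9–15, Week 3 as Days 16–22 and Week 4 as Days 23–29. If treatment did not last 28 days, Week 4 becomes the seven days ending on the last treatment day, wherever these fall.

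**The concern.** Asking for response in two of four weeks is meant to separate sustained benefit from one good week. Two features of the plan can undo that for a patient who stops early. Carrying a good last week forward fills the unobserved weeks with response. Moving Week 4 back to the last treatment days counts an observed week a second time. Either way, a patient with one observed good week can be reported as a responder.

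At stake are four secondary endpoints. Protocol 3.8.1 relies on the relevant secondary endpoints, together with the primary, to show what each component contributes. The trial is open-label, and Protocol 6.14 allows withdrawal for adverse events or lack of efficacy, so stopping could differ between arms. Because the main version is not named, the same patient could also be classified differently in two analyses that both follow the plan.

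**Working it through.** **Inputs.** Protocol 9.2: 132 evaluable and about 155 randomized per group, 15% drop-out. SAP 4.2.2: windows, two-of-four threshold, denominator. Not in the documents: g, the share of drop-outs whose only good week is their last observed week; drop-out by arm; response among completers. These are assumed below.

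**Plan's own figure.** The documents give no figure for the responder endpoints. The drop-out allowance reproduces: 132 / (1 − 0.15) = 155.3, against about 155 stated. Drop-outs per arm: 0.15 × 155 = 23.25, about 23.

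**Step 1: Week 4 for early stoppers under SAP 4.2.2.**

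| Last treatment day | Last complete week | Week 4 becomes | Days shared |
|---|---|---|---|
| 8 | Week 1 (2–8) | 2–8 | 7 of 7 |
| 9 | Week 1 (2–8) | 3–9 | 6 of 7 |
| 15 | Week 2 (9–15) | 9–15 | 7 of 7 |
| 22 | Week 3 (16–22) | 16–22 | 7 of 7 |

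**Step 2: scoring.** A patient stopping after one, two or three complete weeks has 2 + 4 + 8 = 14 possible patterns of good (1) and not good (0) weeks. If unobserved weeks earn nothing, 5 patterns reach two good weeks. Under weekly LOCF 8 do, and under the Week 4 rule without LOCF the same 8 do. The patterns with exactly one good week are:

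| Observed weeks | No credit | Weekly LOCF | Week 4 rule, no LOCF |
|---|---|---|---|
| 1 | 1 | 1 + 3 = 4, responder | 1 + 1 = 2, responder |
| 0, 1 | 1 | 1 + 2 = 3, responder | 1 + 1 = 2, responder |
| 0, 0, 1 | 1 | 1 + 1 = 2, responder | 1 + 1 = 2, responder |
| 1, 0 | 1 | 1 | 1 |
| 1, 0, 0 or 0, 1, 0 | 1 | 1 | 1 |

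The three added patterns are those in which the good week is the last one observed. The table assumes that LOCF acts on weekly averages; neither document says whether it acts on these or on daily scores.

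**Step 3: size in one arm.** Rise in responder rate = 0.15 × g.
- g = 0.25: 3.75 points, 5.8 of 155 patients
- g = 0.50: 7.5 points, 11.6 of 155
- g = 1 (upper bound): 15 points, 23.25 of 155

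**Step 4: difference between arms.** The shift is d₁g₁ − d₂g₂, where d is drop-out. With equal drop-out and equal g it is zero. Illustration: drop-out 20% v 10%, completer response 40% in both arms, the same g in both, and no other drop-out a responder.
- Unobserved weeks as non-response: 0.80 × 0.40 − 0.90 × 0.40 = 0.32 − 0.36 = −4.0 points
- LOCF, g = 0.25: (0.32 + 0.05) − (0.36 + 0.025) = −1.5 points
- LOCF, g = 0.40: (0.32 + 0.08) − (0.36 + 0.04) = 0
- LOCF, g = 0.50: (0.32 + 0.10) − (0.36 + 0.05) = +1.0 point
- LOCF, g = 1: (0.32 + 0.20) − (0.36 + 0.10) = +6.0 points

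**The case against.** **LOCF is not the plan's only rule.** A reader might infer from Protocol 9.9 that LOCF governs every efficacy analysis. The documents do not support that. The preceding sentence of 9.9 says the opposite, its last sentence plans an analysis without replacement, SAP 4.2 runs available data as well, and SAP 4.2.1 makes LOCF a sensitivity analysis for the primary endpoint. This stands. What remains is that no main version is named for the responder endpoints.

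**Removing LOCF would not be enough.** A reader might infer that, without LOCF, a patient stopping on Day 9 after a good Week 1 has one week of four and is a non-responder. Under SAP 4.2.2 that patient's Week 4 is Days 3–9, which shares six days with Week 1, so the count can reach two with no imputation. A single low score on Day 9 could also make Week 2 a responding week, because no minimum number of diary days is set.

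**Part is already settled.** The protocol's 50% of treatment weeks could be read as half of the weeks actually treated. SAP 4.2.2 closes this by naming four weeks, requiring two and dividing by all patients in the arm.

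**No bias between arms is shown.** With 20% v 10% drop-out and g = 0.40, LOCF adds 8.0 and 4.0 points. A reader might take this 4-point gap as a spurious treatment difference. It is a gap in responders added. With 40% completer response, the resulting LOCF rates are equal and it is the non-response rule that gives −4.0 points. This objection stands.

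**Only secondary endpoints are involved.** Also correct. Success rests on the primary sum score, which compares one week with baseline, so no week can be counted twice there.

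**Conclusion.** The concern holds for the four percentage-reduction responder endpoints. Under weekly LOCF, or under the SAP's Week 4 window alone, a patient who stops right after a single good week is scored as meeting a two-week requirement. It does not hold for every drop-out with one good week: that week must be the last one observed. It does not extend to the complete-resolution endpoints, which SAP 4.2.2 scores by days.

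At 15% drop-out, an arm's responder rate rises by 0.15 × g, or 3.75 to 7.5 points for g between 0.25 and 0.50. This assumes that the 15% allowance represents patients who stop during treatment and stay in the FA denominator, that they stop after complete weeks, and that carry-forward is weekly. The value of g is an assumption. The treatment difference shifts only if drop-out or g differs by arm, and its direction cannot be predicted from the documents. The point warrants a change to the plan but does not threaten the trial's main conclusion.

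**What to change.** In SAP 4.2.2 and Protocol 9.9, name one main rule for these four endpoints:

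- Fixed windows for every patient: Days 2–8, 9–15, 16–22 and 23–29. Each diary day is used once, and earlier days are never reused as Week 4.
- A week counts as responding only if it has a stated minimum of diary days (for example 4 of 7) and meets the threshold.
- A week with too few diary days counts as non-response.
- All FA patients stay in the denominator.
- A responder has at least two observed responding weeks of four.

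Keep the LOCF and available-data versions as sensitivity analyses, and state whether LOCF acts on daily scores or weekly averages.

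A minimum of 4 of 7 would not penalise completers who attend Visit 3 a day early within the ±1 day window: Days 23–27 alone give five entries.

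The cost is SAP and protocol wording and a few lines of code. Reported responder proportions become slightly lower. Sample size, conduct, the primary endpoint and the success criterion do not change.
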